9.1.3.4 Rounding

For the calculation of summary statistics and statistical analysis, unrounded data will be used.

In listings, data will be presented with the same precision as the original data at the time of creating the output, unless otherwise specified. Derived data will be rounded for presentation purposes.

For all summaries, mean, standard deviation, percentage, quartiles, median absolute deviation (MAD) and median will be presented to one decimal place greater than the original data and the minimum and maximum will be presented to the same number of decimal places as the original data.

9.1.3.5 Sort Order for Listings

Data will be presented in listings, sorted by patient, day and study visit, unless otherwise specified. All unscheduled assessments will be included in the listings.

9.1.4 Definitions for Statistical Data Analysis

For periodontal parameters:

Six sites per tooth are to be evaluated. At least 4 of the 6 sites per tooth must be evaluated and have the measurements recorded for the tooth to be included in the assessment. If the site is evaluated and there is no PD to measure, the site must be recorded as 0 to indicate that there was no PD at the site (and to distinguish it from a site that was not evaluated).

When less than 4 sites are recorded, the assessment of the tooth will be considered as missing, and all periodontal assessments for that tooth will be excluded from the calculation of the means over all teeth (see Section 5.1.1).

For BoExp parameters:

Values below the lower limit of quantification (LLOQ) will be imputed using LLOQ/2. For

Confidentiality Statement

Data and information contained in this document are considered to constitute trade secrets and confidential commercial information, and the legal protections provided to such trade secrets and confidential information are hereby claimed under the provisions of applicable law. No part of this document may be publicly disclosed without the written consent of Philip Morris Products S.A.

values above the upper limit of quantification (ULOQ), the ULOQ will be imputed.

The number of values below LLOQ or above ULOQ will be presented in each summary table. If more than 50% of the data are below LLOQ, only the number and percentage of values below LLOQ will be reported in the summary together with the minimum and maximum values.

For calculation of creatinine adjusted BoExp if the denominator is below LLOQ then the ratio will not be calculated and will be tabulated as “Not Calculated” in descriptive summaries and excluded from the main analysis.

For self-reported tobacco or nicotine containing tobacco product use over the duration of the study data:

Only available data will be included in the product use summaries. Overall product exposure groups will be defined based on the data collected from randomization until EOS.

9.1.5 Handling of Dropouts or Missing Data

9.1.5.1 Drop Out (withdrawal)

Subjects who dropped out from the study in any way will have their data analyzed up to the point of last contact.

9.1.5.2 For Missing or Partial Dates

Missing dates for Visits after randomization will be imputed by adding nominal days to the date of randomization. If the imputed date falls after EOS date (e.g. for early terminated subjects), then the end of study date will be used.

Partial dates will not be imputed for Adverse Events (AEs), for medical history, and for concomitant medications, but assumptions will be made as follows to assign them to specific analysis categories:

Date information	AE data	Medical History/Concomitant Disease data	Prior and Concomitant Medication data
Missing or Partial date (e.g., --May2012, or ----2011). If month/year is the same as, or later than the month and/or year of Screening.	Included in summaries	Concomitant disease (included in summaries)	Concomitant Medication (included in summaries)
Partial date, (e.g., --May2012, or ----2011). If month and/or	Listings	Medical history	Prior medication

Confidentiality Statement

Data and information contained in this document are considered to constitute trade secrets and confidential commercial information, and the legal protections provided to such trade secrets and confidential information are hereby claimed under the provisions of applicable law. No part of this document may be publicly disclosed without the written consent of Philip Morris Products S.A

year is earlier than the month and/or year of Screening.	only	(included in summaries)	(included in summaries)
--	------	-------------------------	-------------------------

9.1.6 Handling of Unplanned Data

All data collected on scheduled visits will be used for tables. Therefore data collected on unscheduled visit will be excluded from tables, however included in listings (no time window will be considered).

9.1.7 Multicenter Studies

The study will be conducted at multiple centers. In order to consider the effects on the endpoint analysis caused by site, site will be included as a random effect in statistical model. Detail will be described in 9.5.1.

9.1.8 Multiple Comparison/Multiplicity

There will be an adjustment for multiplicity for the secondary testing of CAL and PD within the As Exposed Set, as well as for BoExp. PD at 3 months and CAL at 6 and 3 months will be tested in a hierarchical manner, depending on the outcome of the test at previously specified endpoint in hierarchical testing order. The order of testing is as follows,

The primary analysis, of PD at 6 months will be tested using a one-sided alpha level of 2.5%.

1. PD at 6 months will be tested.

The secondary analysis of PD at 3 months and CAL at 6 and 3 months will be tested in a hierarchical manner, using a one-sided alpha level of 2.5%, depending on the outcome of the test at previously specified endpoint in hierarchical testing order.

1. PD at 3 months will be tested only if the test for PD at 6 months is significant.

2. CAL at 6 months will be tested only if the test for PD at 3 months is significant

3. CAL at 3 months will be tested only if the test for CAL at 6 months is significant.

Additional secondary analysis of the BoExp will be tested, in a hierarchical manner within each BoExp (independent of the other statistical tests being performed), using a one-sided alpha level of 2.5%. The hierarchical order will be:

1. BoExp at 6 months will be tested.

2. BoExp at 3 months will be tested only if the test for BoExp at 6 months is significant.

Total NNAL and CEMA levels (concentration data adjusted for creatinine), analyzed on a logarithmic scale, will be tested at 6 and then 3 months, in that order, so that the testing of each BoExp will stop if the test is not significant.

Confidentiality Statement

Data and information contained in this document are considered to constitute trade secrets and confidential commercial information, and the legal protections provided to such trade secrets and confidential information are hereby claimed under the provisions of applicable law. No part of this document may be publicly disclosed without the written consent of Philip Morris Products S.A

Unless stated otherwise, all statistical tests will be one-sided and conducted at the 2.5% level, and all CIs will be two-sided 95%.

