PMI has undertaken a comprehensive assessment program on IQOS, including pre-clinical and clinical studies, aiming to demonstrate that IQOS is a reduced risk product. The non-clinical assessment of IQOS, consisting of the aerosol chemistry analysis, *in vitro* and *in vivo* studies, supported the initiation of clinical studies, as no new or increased toxicological hazard in the product's aerosol was detected when compared with cigarette smoke. Results from pre-clinical *in vivo* studies comparing cigarette smoke with IQOS aerosol in continuous inhalation show that exposure to IQOS aerosol, at multiple concentrations, results in a dramatically lower systemic toxicity, extensively reduced lung inflammation and reduced histopathological changes in the nasal epithelium as well as lung tissue compared to cigarette smoking [62, 63]. Furthermore, exposure to IQOS aerosol in mice does not enhance cardiovascular disease or emphysema, as cigarette smoke does, and switching from cigarette smoke to IQOS aerosol exposure halts of *e.g.*, aortic plaque growth in a similar manner as smoking cessation [64, 65]. Recent non-clinical data on human organotypic buccal epithelial cultures demonstrated that acute exposure to IQOS aerosols, when compared to cigarette smoke, had overall a significantly lower impact on buccal epithelial physiology [66]. Unlike cultures exposed to cigarette smoke, IQOS aerosol-exposed cultures showed no cytotoxicity, regardless of exposure, concentration, or time, and tissue damage was minimal, with no apical keratinization, intracellular granular structure, or loss of structural integrity. Furthermore, levels of pro-inflammatory mediators were significantly modulated in cigarette smoke-exposed cultures (*e.g.*, increased VEGF-A, TGF $\alpha$ , MMP-1, IL1 $\beta$  and decreased Chemokine [C-X-C motif] ligand 10 [CXCL10], Chemokine [C-X-C motif] ligand 8 [CXCL8], CSF-2, and IL-6) and to a much lesser extent in IQOS.

Several clinical studies have been conducted with IQOS, in Europe, Asia and the United States, in order to evaluate the nicotine pharmacokinetics (PK) profile [67-70], to demonstrate reduced exposure [71-74], and to determine functional and biological changes when adult smokers

---

 Reduced risk products (“RRPs”) is the term used by PMI to refer to products that present, are likely to present, or have the potential to present less risk of harm to smokers who switch to these products versus continued smoking

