### 3.3 Exploratory Objectives and Endpoints

1. To determine quantitative changes in the inflammatory response by measuring pro-inflammatory and immuno-regulatory mediators in the GCF in patients switching to IQOS use compared to those continuing to smoke cigarettes.

Endpoints (3 months):

- Measurement of pro-inflammatory and immuno-regulatory mediators in the GCF .

2. To evaluate the microbiological status in patients switching to IQOS use compared to those continuing to smoke cigarettes. 

Endpoint (6 months):

- Microbiological status from SP samples.

---

 sCD40L, CRP, EGF, Eotaxin/CCL11, Flt3 ligand, GM-CSF, GRO, IFN $\alpha$ 2, IL-1 $\alpha$ , IL-1 $\beta$ , IL-1Ra, IL-2, IL-3, IL-4, IL-5, IL-6, IL-7, IL-8/CXCL8, IL-9, IL-10, IL-12 (p40), IL-12 (p70), IL-13, IL-15, IL-17A/CTLA8, IP-10/CXCL10, MCP-1/CCL2, MCP-3/CCL7, MDC/CCL22, MIP-1 $\alpha$ /CCL3, MIP-1 $\beta$ /CCL4, MMP-1, MMP-8, MMP-9, MMP-10, MMP-12, MMP-13, osteoprotegerin, PDGF-AA, PDGF-AB/BB, RANKL, RANTES/CCL5, TGF $\alpha$ , TIMP-1, TNF $\alpha$ , TNF $\beta$  / LT- $\alpha$ , (please refer to the Abbreviations for full spelling).

 Results of these exploratory objectives will be reported in separate reports, and will not be part of the main clinical study report.

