### 7.5.3 Assessments in GCF

GCF will be collected from 4 target sites at V2 and V3. The sampling should be performed before periodontal assessments. The selection of the target sites is described in section 7.3.5.2).

At the time of the analysis, in order to characterize the inflammatory response, immunoregulatory mediators in GCF  will be measured with two types of technologies, *i.e.*, bead-based multiplex assays (MAP) using the Luminex technology or targeted mass spectrometry.

Targeted mass spectrometry analysis will be performed using the quantitative parallel reaction monitoring (PRM) where the unique peptides of the selected protein targets will be analyzed for absolute quantitation in reference to a synthetic unique peptide of the selected protein

---

 sCD40L, CRP, EGF, Eotaxin/CCL11, Flt3 ligand, GM-CSF, GRO, IFN $\alpha$ 2IL-1 $\alpha$ , IL-1 $\beta$ , IL-1Ra, IL-2, IL-3, IL-4, IL-5, IL-6, IL-7, IL-8/CXCL8, IL-9, IL-10, IL-12 (p40), IL-12 (p70), IL-13, IL-15, IL-17A/CTLA8, IP-10/CXCL10, MCP-1/CCL2, MCP-3/CCL7, MDC/CCL22, MIP-1 $\alpha$ /CCL3, MIP-1 $\beta$ /CCL4, MMP-1, MMP-8, MMP-9, MMP-10, MMP-12, MMP-13, osteoprotegerin, PDGF-AA, PDGF-AB/BB, RANKL, RANTES/CCL5, TGF $\alpha$ , TIMP-1, TNF $\alpha$ , TNF $\beta$  / LT- $\alpha$  (please refer to the Abbreviations for full spelling)

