#### 12.9.2 Descriptive Analysis

The analysis for the exploratory endpoints of cytokine/chemokine (MAP) and targeted unique peptides (PRM) will follow the statistical approach described for the secondary endpoints and include descriptive and inferential statistics. Descriptive statistics will be reported by treatment group and strata, and will include basic descriptive statistics such as the sample size, the sample mean, standard deviation, standard error of the mean, and CV. Robust measures for the center (median) and the dispersion (median absolute deviation, MAD) of the data will be also included. Inferential statistics will focus on treatment group differences and will take into account stratification criteria as well as repeated measurements. The general statistical linear mixed model developed for the primary endpoint may be used if necessary for the exploratory endpoints in order to test treatment differences and to adjust for stratification factors and repeated measurements. For the exploratory endpoints, a two-sided alternative for the differences between groups will be tested on the 5% type I error rate, while no adjustment for multiplicity will take place. The null hypothesis tested will be that all means of groups tested for a given variable are equal. The alternative hypothesis is that at least one of the means is different from the others. Further details will be specified in the SAP.

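### SAP 9.5.3 departs from the protocol on the exploratory GCF mediators: its default makes the tests one-sided where the protocol says two-sided, and it lists a visit (V4) at which no GCF is collected

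*SAP*

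**What the plan says.** **Timing.** The GCF endpoint is at 3 months in both documents (protocol 3.3, SAP 3.3). Protocol 7.5.3 says "GCF will be collected from 4 target sites at V2 and V3". The Appendix 1 schedule marks the same two visits, and the V4 procedures in protocol Table 6 contain no GCF collection. SAP 2.1.1 sets the GCF baseline at V2. SAP 9.5.3 nevertheless gives V3 and V4 as target visits for the multiplex and mass-spectrometry model, and baseline, V3 and V4 for the summary table. The model includes visit, visit-by-product use and a Toeplitz covariance.

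**Sidedness.** Protocol 12.9.2 says "For the exploratory endpoints, a two-sided alternative for the differences between groups will be tested on the 5% type I error rate", without multiplicity adjustment. It adds that "The null hypothesis tested will be that all means of groups tested for a given variable are equal". The protocol has its own one-sided default in 12.1.5, so 12.9.2 is a stated exception. SAP 9.1.8 repeats the default, "Unless stated otherwise, all statistical tests will be one-sided and conducted at the 2.5% level", and makes all confidence intervals two-sided 95%. SAP 9.5.3 states neither sidedness nor alpha and refers to the primary analysis for its code. That code (SAP 9.5.1.1) carries `ALPHA=0.025` and `UPPER`. SAP section 7 declares two changes from the protocol, both to analysis sets; neither concerns GCF visits or sidedness.

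**The concern.** Someone programming from the SAP alone would run upper-tail tests at 2.5% on every mediator, though the protocol asks for a non-directional comparison. For pocket depth, one direction is clearly favourable and the hypotheses say so. For the mediators, nothing in either document says which direction is of interest.

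A single tail would not suit the panel in any case. Protocol 2.1 reports, from buccal tissue cultures, that "levels of pro-inflammatory mediators were significantly modulated in cigarette smoke-exposed cultures", with some mediators rising and others falling.

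The V4 entries suggest that 9.5.3 was adapted from the primary analysis without being fitted to the GCF schedule. Its last model-building step still speaks of estimating PD.

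At stake is a clear reading of the only exploratory objective that SAP 3.3 assigns to the clinical study report.

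**Working it through.** **1. The two error rules**
- Protocol 12.9.2: 5% in total, 2.5% in each tail, reject if |z| > 1.96.
- SAP 9.1.8 default: 2.5% in one tail, reject if z > 1.96.

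The cut-off is the same, so the difference is the missing tail. Under a global null with 46 independent or dependent tests (one comparison, one time point), the expected number of false positives is 46 × 0.05 = 2.3 under the protocol and 46 × 0.025 = 1.15 under the default. The count of 46 comes from the analyte footnote to protocol 3.3.

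**2. Rejection in the untested direction**

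For a standardised difference d with n per group, the normal approximation has mean shift d/√(2/n). The upper-tail test rejects with probability 1 − Φ(1.96 − d/√(2/n)). At d = 0 this is 2.5%, and for any negative d it is smaller. So the range is 0 to 2.5%, whatever n and d are.

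An illustration needs assumed values. I take n = 64, the protocol's evaluable number per arm for pocket depth, and d = 0.5.
- The plan's figure reproduces: 2 × (1.960 + 0.842)² × (0.5/0.25)² = 62.8, so 63 by the normal approximation; the t-test version gives 63.8, so 64. Then 64/0.75 = 85.3, so 86 per arm and 172 in total.
- Shift: 0.5/√(2/64) = 0.5/0.1768 = 2.828.
- Tested direction: 1 − Φ(1.96 − 2.828) = 0.807 under either rule.
- Opposite direction, one-sided: 1 − Φ(1.96 + 2.828) = 8.4 × 10⁻⁷.
- Opposite direction, two-sided: 0.807.
- Noncentral-t values are 0.801 in place of 0.807, and about 9 × 10⁻⁷ in place of 8.4 × 10⁻⁷.

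**3. Test against interval**

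A two-sided 95% interval excludes zero exactly when the two-sided 5% test rejects. The upper-tail 2.5% test rejects only when the lower limit is above zero. When the upper limit is below zero, the interval shows a difference and the test does not.

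**4. Direction**

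In protocol 2.1, smoke raised TGFα, MMP-1 and IL-1β and lowered CXCL10, CXCL8 and IL-6. All six are in the GCF panel. These are culture data, so they do not predict GCF results, but they show why one common tail has no basis. The protocol's null of equal means across groups has no direction either.

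**5. The V4 terms**

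With V2 as baseline and V3 as the only later sample, visit has one level. Visit then duplicates the intercept, and visit-by-product duplicates product use. With one record per patient, the Toeplitz matrix reduces to a single residual variance. The V4 rows of the tables have no data.

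**The case against.** **The protocol may still govern sidedness.** The SAP default yields where something else is stated, the SAP describes itself as supplementing the protocol analysis, and section 7 lists no change to exploratory testing. On that reading, protocol 12.9.2 is the exception. This is coherent, so a reader should not infer that the SAP expressly chooses one-sided tests; it reaches them by default and by borrowed code. But 12.9.2 leaves further detail to the SAP, and the SAP's code points the other way. The ambiguity remains and one sentence removes it.

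**The intervals would show the effects.** A reader might infer that changes in the untested direction would be invisible in the study report. The documents do not support that: 9.5.3 requires a 95% interval for each difference in least-squares means, and 9.1.8 makes it two-sided. The loss is confined to the formal tests and their agreement with the intervals.

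**The V4 error is largely harmless numerically.** This stands. With no V4 records the fit collapses to V3, and no bias or wrong estimate follows. SAP 3.3 and 2.1.1 leave the intended time point clear.

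**There may be repeated records per patient.** GCF comes from four target sites, and the documents do not say whether these are pooled or assayed separately. Protocol 12.9.2 also asks for repeated measurements to be taken into account. This stands, and it limits how far the model should be simplified.

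**The power figures are illustrative.** This also stands. The analysis compares three product-use groups of unknown size, and no effect size is documented for any mediator.

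**Conclusion.** SAP 9.5.3 should be corrected on both counts. Taken on its own text, it would apply directional tests to 46 analytes with no stated direction, contrary to the protocol and without declaring the change. It also plans model terms and tables for V4 GCF data that will not exist.

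For sidedness, the size is that any effect in the untested tail has less than a 2.5% chance of rejection. The near-zero figure in the illustration rests on the assumed 64 per group and 0.5 SD and is not a property of this trial. The conclusion also assumes that the 9.1.8 default is applied where 9.5.3 is silent.

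For V4, the size is empty outputs and redundant terms, not a biased estimate.

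The impact is limited to the exploratory GCF analysis. The primary and secondary tests and the sample size are untouched.

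**What to change.** In SAP 9.5.3:
- State that the mediator tests are two-sided at 5%, as in protocol 12.9.2, with two-sided 95% confidence intervals.
- Do not carry over `ALPHA=0.025` and `UPPER` from the primary sample code.
- Delete V4 from the model's target visits and from the summary table, and align the related table shells and heatmaps.
- Fit the model at V3 only, removing visit, visit-by-product use and the across-visit Toeplitz structure. Keep the other listed covariates and site as a random effect.
- State whether the four target sites are pooled or assayed separately, and keep a within-patient term only if they are assayed separately.

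In SAP 9.1.8, exempt exploratory endpoints from the one-sided default. If one-sided testing is in fact intended, give a direction for each analyte and declare and justify the change in section 7.

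The cost is a few sentences and simpler code, with no new data and no change to sample size.

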9.2 Disposition of Subjects

Summary Table of Subject Disposition	
Population	: All subjects screened
Contents	: 
 • All subjects screened • All screen failure subjects (include subjects who were enrolled but not randomized) 
 ➤ Primary reason for screen failure • All subjects randomized 
 ➤ Randomized (IQOS/Cigarettes) ➤ Completed subject ➤ Discontinued subject • Reason of discontinuation
Remarks	: Percentage will be presented for disposition events after randomization and the denominator will be the number of subjects randomized into each arm.
Output	15.2.1.1 Summary Table of Subject Disposition - All Subjects Screened - 15.3.1.1 Listing of Subject Disposition - All Subjects Screened - 15.3.1.2 Listing of Screen Failed Subjects and Reason - All Subjects Screened - 15.3.1.3 Listing of Informed Consent - All Subjects Screened -

9.3 Demographic and Other Baseline Characteristics

Summary Table of Analysis Sets	
Population	: All subjects randomized 
 ➤ Randomization arm ➤ Product use pattern categories
Contents	: The number and percentage of subjects of analysis set defined in “ population ” will be presented.

Confidentiality Statement

Data and information contained in this document are considered to constitute trade secrets and confidential commercial information, and the legal protections provided to such trade secrets and confidential information are hereby claimed under the provisions of applicable law. No part of this document may be publicly disclosed without the written consent of Philip Morris Products S.A

Output	
15.2.2.1 Summary Table of Analysis Sets by Randomization Arm - Randomized Subjects -
 
15.2.2.2 Summary Table of Analysis Sets by Product Use Categories - Randomized Subjects -
 
15.3.2.1 Listing of Analysis Sets - Randomized Subjects -

--------	---

Summary Table of Demographics	
Population	
 • As Exposed Set 
 ➤ Product use pattern categories • Full Analysis Set 
 ➤ Randomization arm • Per Protocol Set 
 ➤ Randomization arm • Safety Set 
 ➤ Product use pattern categories
Contents	: Refer to Descriptive statistics
Analysis variables	
 • Age [years] • Age ($30 \leq <40$, $40 \leq <50$, $50 \leq <60$, $60 \geq$) • Sex (Male, Female) • Race (Asian, Black or African American, White, Native Hawaiian or Other Pacific Islander, American Indian or Alaska Native) • Nationality (Japanese) • Daily cigarette consumption over the month prior to V1 (10-19 cigarettes/day, > 19 cigarettes/day) • Disease severity in smokers with generalized chronic periodontitis ($PD < 5\text{mm}$, $PD \geq 5\text{mm}$) • Cotinine (Negative < 200 ng/mL, Positive ≥ 200 ng/mL)
	
 • Use the value of age from SDTM datasets. • Denominator will be the number of subjects in the target population. For the race, no percentage will be calculated since multiple selections are permitted.
Output	15.2.2.3 Summary Table of Demographics by Product Use Categories - As Exposed Set -

Confidentiality Statement

Data and information contained in this document are considered to constitute trade secrets and confidential commercial information, and the legal protections provided to such trade secrets and confidential information are hereby claimed under the provisions of applicable law. No part of this document may be publicly disclosed without the written consent of Philip Morris Products S.A

	15.2.2.4 Summary Table of Demographics by Randomization Arm - Full Analysis Set, Per Protocol Set, Safety Set - 15.3.2.2 Listing of Demographics - As Exposed Set -
--	--

Summary Table of Smoking History	
Population	: 
 • As Exposed Set 
 ➤ Product use pattern categories • Full Analysis Set 
 ➤ Randomization arm • Per Protocol Set 
 ➤ Randomization arm
Contents	: Refer to Descriptive statistics
Analysis variables	: 
 • Smoked for at least the past 5 consecutive years • Number of cigarettes smoked per day over the last 5 years [cig/day] • Number of menthol cigarettes per day [cg/day] • Number of years of smoking history [years] • Number of cigarettes smoked per day after starting smoking [cig/day]
Output	15.2.2.5 Summary Table of Smoking History by Product Use Categories - As Exposed Set - 15.2.2.6 Summary Table of Smoking History by Randomization Arm - Full Analysis Set, Per Protocol Set - 15.3.2.3 Listing of Smoking History - As Exposed Set - 15.3.2.4 Listing of Starter Kit Information - As Exposed Set -

Summary Table of Baseline Characteristics of Periodontal Disease	
Population	: 
 • As Exposed Set 
 ➤ Product use pattern categories
Contents	: Refer to Descriptive statistics. Calculate the descriptive statistics by

Confidentiality Statement

Data and information contained in this document are considered to constitute trade secrets and confidential commercial information, and the legal protections provided to such trade secrets and confidential information are hereby claimed under the provisions of applicable law. No part of this document may be publicly disclosed without the written consent of Philip Morris Products S.A

Summary Table of Baseline Characteristics of Periodontal Disease	
	Cigarette Consumption Prior to V1, Pocket Depth at V1, and overall for each analysis item.
Analysis variables	: 
 • Teeth Count • Pocket Depth (mm) • Clinical Attachment Loss (mm) • Bleeding on Probing (%) • Gingival Index • Plaque Control Record (%)
Output	15.2.2.7 Baseline Characteristics of Periodontal Disease - As Exposed Set -

Summary Table of Medical History	
Population	: 
 • Safety Sets 
 ➤ Product use pattern
Contents	: The number and percentage of patients experiencing medical history and the number of medical history will be counted by Medical Dictionary for Regulatory Activities (MedDRA, Version 20.0 or higher) System Organ Class (SOC) term and Preferred Term (PT). All cases collected on the form for medical history of CRF (MHCAT="MEDICAL HISTORY") will be tabulated.
Definition	: Medical history is defined as any condition that started and ended prior to ICF signature.
Remark	: SOC and PT will be sorted by alphabetical order.
Output	15.2.3.1 Summary Table of Medical History - Safety Set - 15.3.3.1 Listing of Medical History/ Concomitant disease and Periodontal Disease - Safety Set -

Summary Table of Periodontal Disease History

Confidentiality Statement

Data and information contained in this document are considered to constitute trade secrets and confidential commercial information, and the legal protections provided to such trade secrets and confidential information are hereby claimed under the provisions of applicable law. No part of this document may be publicly disclosed without the written consent of Philip Morris Products S.A

Summary Table of Periodontal Disease History	
Population	: 
 • Safety Sets 
 ➤ Product use pattern
Contents	: The number and percentage of patients experiencing periodontal disease and the number of periodontal disease history will be counted by Medical Dictionary for Regulatory Activities (MedDRA, Version 20.0 or higher) SOC and PT. All cases collected on the form for periodontal disease history (MHCAT=" PERIODONTAL DISEASE HISTORY") will be tabulated.
Definition	: Periodontal disease history is defined as any condition that started and ended prior to ICF signature.
Remark	: SOC and PT will be sorted by alphabetical order.
Output	15.2.3.3 Summary Table of Periodontal Disease History - Safety Set -

Summary Table of Concomitant Disease	
Population	: 
 • Safety Sets 
 ➤ Product use pattern
Contents	: The number and percentage of patients experiencing concomitant disease and the number of concomitant disease will be counted by Medical Dictionary for Regulatory Activities (MedDRA, Version 20.0 or higher) SOC and PT. All cases collected on the form for concomitant disease (MHCAT=" CONCOMITANT DISEASE") will be tabulated.
Definition	: A concomitant disease is defined as any condition that started prior to ICF signature and is still ongoing at the end of V1.
Remark	: SOC and PT will be sorted by alphabetical order.
Output	15.2.3.2 Summary Table of Concomitant Disease - Safety Set -

Confidentiality Statement

Data and information contained in this document are considered to constitute trade secrets and confidential commercial information, and the legal protections provided to such trade secrets and confidential information are hereby claimed under the provisions of applicable law. No part of this document may be publicly disclosed without the written consent of Philip Morris Products S.A

